## 1530 **4.7.2. Participant Selection**

1531 See Section 4. for eligibility criteria.

1532

## **4.7.3. Data Elements**

Serum tests of liver function at defined times will be tabulated and compared sequentially
for donors and LDLT recipients. Mean values for comparable time points will be
compared between DDLT and LDLT.

1537

To correlate liver function in donors with long-term health outcomes as determined by data collection at defined intervals as noted above in Aim 3 and the incidence of clinical complication

1541

To correlate success or failure of regeneration with a series of selected clinical and laboratory variables in donors and recipients. Liver volume at defined intervals will be correlated with a selection of pre, peri, and post surgical clinical and laboratory variables

1545

#### 4.7.4. Sample Size and Power Calculations

Power analyses are based on estimation of correlation coefficients and coefficient of determination between measures of liver regeneration and liver function. We anticipate having 360 donors and 360 recipients in the Cohort study. We assume a two-sided test for a non-zero correlation with significance level 0.05. With these assumptions, we can detect a correlation of 0.17 or greater with 90% power in either the donors or the recipients. In a multiple regression analysis, we will have 85% power to detect an increase in the R-squared of 2%, assuming 5 variables already in the model explaining

1553 20% of the variance.

## 1554 4.7.5. Statistical Analysis

1555 Analysis of liver regeneration will be performed using repeated measures regression. We 1556 will follow the mean course of hepatic function and mass in living donors from baseline 1557 through 3 months post surgery. We will test for a difference between liver function at baseline and function at 3 months post surgery to determine whether liver function has 1558 1559 returned to normal. We will also model liver function as predicted by liver regeneration 1560 volume, biochemical impairment, and the occurrence of certain clinical events. We will 1561 also compare the return of hepatic function in LDLT versus DDLT recipients using 1562 repeated measures regression. 1563

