202 203 204 205 206 207 208 209	
 
Primary Objective
 
1. To measure hepatic function and mass in living donors at enrollment, intraoperatively, and following hepatectomy, in order to determine whether return of hepatic function following donation correlates with rate of liver volume regeneration, biochemical impairment, and clinical events, and to see whether return of function is complete by 3 months post-resection.
 

210 211 212 213 214 215 216 217 218 219	
 
Secondary Objectives         
 
To correlate liver function in donors with long-term health outcomes and the incidence of clinical complications.
 
To correlate success or failure of regeneration with a series of selected clinical and laboratory variables in donors and recipients.
 
To collect liver biopsy and serum samples prospectively from a large series of donors and recipients which may form the basis for subsequent characterization of protein and gene expression of selected inflammatory and growth-related molecules.
 
 
 

220 221	3.8. Secondary Aim 4: To evaluate differences in the immune response to LDLT vs. DDLT grafts.
222 223 224 225 226 227	
 
Primary objectives
 
1. To determine whether LDLT, which is associated with a regenerating liver, meaningfully increases the incidence of clinical rejection. In the cohort, we will compare the incidence of immunologic complications, specifically the incidence and severity of rejection between LDLT and DDLT in a defined set
 

-	Deviced Calcert Protocol 02100(

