800 801 802 803 804 805 806 807 808 809 810 811 812 813 814	
 
Donor satisfaction will be related to both the medical and quality of life experiences of the recipient. This linkage will be greater for spouses.
 
Pre-donation, donor physical and mental QOL will be above the norm of the general population. One or more years post-donation, donor QOL will remain in the normal range of the population.
 
Donors with strong social support will feel less of a sense of abandonment.
 
Donors with a better understanding of the risks of the procedure will have greater acceptance post-donation.
 
Donors will have comparable QOL post-donation compared with controls who did not donate.
 
Sexual satisfaction and comfort with body image will be more positive for those with strong social support and a better understanding of their post-operative course.
 

815

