#### 4.7. Secondary Aim 3: To systematically characterize liver regeneration and function in donors and recipients.

1454 Information about liver regeneration after liver transplantation remains descriptive and is 1455 limited by our inability to directly sample liver tissue in the days after liver surgery. 1456 Following donation and transplantation, it has been observed that hepatic function of 1457 living liver donors returns to normal soon after right hepatic lobe resection using standard 1458 serum tests of liver function. Recipients of living donor liver transplants also have rapid 1459 return of function, however there may be a reduction and delay in recovery of hepatic 1460 metabolism following LDLT compared to whole DDLT, which has been observed with 1461 respect to the metabolism of immunosuppressive compounds.

1462

1463 Regeneration may fail if the graft is excessively small or damaged in other ways though 1464 the factors associated with graft function have not been adequately studied. Finally, it 1465 remains uncertain when and if the liver volume returns to its baseline following this 1466 procedure.

1467

1468 Initiation of molecular pathways associated with liver regeneration previously identified

1469 in rodent models is presumably necessary for hepatic recovery in the human living donor

- 1470 liver transplant setting in both donors and recipients. It is presumed that failure of
- 1471 regeneration is a consequence of a failure to initiate these events though limitations in our
- 1472 ability to directly assess liver tissue over time has prevented confirmation of these expectations.
- 1473

1475 Primary Objectives

14/5	Primary Objectives
1476	• To measure hepatic function and mass in living donors at study entry,
1477	perioperatively, and following hepatectomy, and determine whether return of
1478	hepatic function following donation correlates with rate of liver regeneration,
1479	biochemical impairment, and clinical events, and if return of function is complete
1480	by 3-6 months post-resection.
1481	• To correlate liver function in donors with long-term health outcomes and the
1482	incidence of clinical complications.
1483	
 
To correlate success or failure of regeneration with a series of selected clinical
 

1484	and laboratory variables in donors and recipients
1485	
 
To collect liver biopsy and serum samples prospectively from a large series of
 

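### A test for a difference between baseline and month 3 cannot establish that donor liver function has returned to normal, and Section 4.7.5 gives no other rule

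*Protocol*

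**What the plan says.** Section 4.7.5 (Secondary Aim 3, regeneration) plans a repeated measures regression that "will follow the mean course of hepatic function and mass in living donors from baseline" through 3 months. It then plans a test for a difference between liver function at baseline and "function at 3 months post surgery to determine whether liver function has" returned to normal.

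The objective served is the primary objective of the aim. Section 3.7 words its last part as "whether return of function is complete by 3 months post-resection". Section 4.7 restates it as complete "by 3-6 months post-resection".

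Section 4.7.4 anticipates "360 donors and 360 recipients in the Cohort study". Its power statements concern only correlations and increases in R-squared. Sections 4.7 to 4.7.5 contain no margin, no confidence-interval rule, no reference range for normal, no SD of change and no criterion for recovery in an individual donor.

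**The concern.** Whether return of function is complete is a question about the absence of a meaningful deficit. A test for a difference takes no change as its null hypothesis. Rejection shows that the mean moved by some amount, possibly trivial. Failure to reject shows only that the data did not settle the matter. The sentence in 4.7.5 nevertheless gives this test the job of deciding whether function is back to normal.

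Two things follow. The answer depends on how many donors have month-3 data, and sparse follow-up pushes it towards apparent recovery, which is the unsafe direction. With complete follow-up, a shift too small to matter could be read as incomplete recovery. Section 4.3 lists inadequate hepatic reserve among the unanswered risks to the donor, so a loosely drawn conclusion here could be used to reassure future donors.

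**Working it through.** **Inputs from the protocol.** 360 donors; two-sided 5% level (both Section 4.7.4, stated for the correlation test).

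**Assumptions.** Shifts and margins are in SDs of the within-donor change from baseline to month 3. The comparison is treated as a paired test. Evaluable numbers of 180 and 90 are illustrative, as are all the margins. The protocol supplies none of these.

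**The plan's own figure.** Section 4.7.4 states 90% power for a correlation of 0.17. With Fisher's z, power = Phi(atanh(0.17) × sqrt(357) − 1.96) = Phi(3.244 − 1.96) = 90.0%. It reproduces, but it does not concern the recovery test, for which no power or margin is stated.

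**Smallest significant shift.** At n = 360 the 95% interval half-width is 1.96 / sqrt(360) = 0.103 SD. Any observed mean shift beyond about 0.10 SD is therefore significant.

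**Chance that a true shift d is declared a difference at n = 360.** Power = Phi(d × sqrt(n) − 1.96).
- d = 0.10: Phi(1.897 − 1.96) = 47.5%
- d = 0.17: Phi(3.226 − 1.96) = 89.7%
- d = 0.20: Phi(3.795 − 1.96) = 96.7%

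**Chance that a true deficit of 0.20 SD is missed.**

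| Evaluable donors | 0.20 × sqrt(n) | Power | Missed |
|---|---|---|---|
| 360 | 3.795 | 96.7% | about 3% |
| 180 | 2.683 | 76.5% | about 24% |
| 90 | 1.897 | 47.5% | about 52% |

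The normal approximation is used throughout. The noncentral t distribution changes these figures by no more than about one percentage point.

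**The alternative.** Two one-sided 5% tests against a margin m, no true change: power = 2 × Phi(m × sqrt(n) − 1.645) − 1.
- n = 360, m = 0.20: 2 × Phi(2.150) − 1 = 97%
- n = 360, m = 0.15: 2 × Phi(1.201) − 1 = 77%
- n = 360, m = 0.10: 2 × Phi(0.252) − 1 = 20%
- n = 180, m = 0.20: 2 × Phi(1.038) − 1 = 70%
- n = 90, m = 0.20: 2 × Phi(0.252) − 1 = 20%

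If the true shift is 0.10 SD, power at n = 360 and m = 0.20 falls to 60%. Under this rule fewer data make a conclusion of recovery harder to reach, and a true deficit equal to the margin is passed at most about 5% of the time at any n.

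**Time point.** Sections 3.7 and 4.7.5 say 3 months; Section 4.7 says 3 to 6 months. For data near month 6, Section 4.7.1 lists serum samples at 24 weeks. Section 4.9.3 says donors have no blood drawn at month 6, and the month-6 column of Appendix B is blank. The donor visit list in Section 4 goes from month 3 to month 12, with post-donation imaging at month 3 only.

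**The case against.** The protocol never writes that a non-significant result counts as recovery or that a trivial shift counts as failure. The test sits within a regression describing the mean course, Section 4.7.3 tabulates values over time, and a difference test can validly show that return is incomplete. All of this is right. But 4.7.5 still ties the test to the conclusion and offers no other route to it, and the affirmative answer is the one the test cannot give.

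Margins are ordinary SAP content, and an SAP may exist. Their absence alone would be no finding. The point is that the protocol has already named a test that does not fit the question.

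The size can be overstated. At the planned 360 donors a 0.20 SD deficit is missed only about 3% of the time, and nothing in the document predicts follow-up as low as 90. Nor does it separate important shifts from unimportant ones, so a 0.10 SD shift cannot be called trivial from the text. The aim is secondary, and its objective is mainly correlational.

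A reader might extend the criticism to donor quality of life, because Section 4.3 includes the hypothesis "Donors will have comparable QOL post-donation compared with controls who did not donate". The documents do not support that. The list is offered as examples, and Section 4.3.5 plans to estimate mean differences between donors and controls; nothing there infers comparability from a non-significant test.

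A reader might also conclude that no donor data are planned near month 6. That goes too far, because Section 4.7.1 schedules 24-week serum. The documents conflict on this.

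**Conclusion.** The point holds for the recovery sentence in Section 4.7.5. As written, the only stated method for deciding whether donor function has returned to normal cannot establish that it has. With complete data the chance of overlooking a 0.20 SD deficit is small. It rises to about 24% with half the donors evaluable and 52% with a quarter. The opposite problem, significance for any observed shift above about 0.10 SD, applies at the full planned number.

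These sizes rest on assumed SD units, a paired comparison and illustrative evaluable numbers; the logical fault does not. It would be wrong to infer that the planned sample suffices for any margin: it does near 0.20 SD if there is no true change, but not near 0.10 SD. This is worth correcting in a secondary aim; it does not threaten the primary aims. The inconsistent time points are a separate, smaller matter.

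**What to change.** In Section 4.7.5, replace the test with an estimate of the mean month-3 minus baseline change and its confidence interval for each liver-function measure, reported whatever the result. Conclude return to baseline only if the interval excludes a deficit larger than a margin that is clinically justified and fixed before analysis. Use a non-inferiority form if only a deficit matters, and two one-sided tests if change in either direction matters.

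Separately, make the objective's time point agree across Sections 3.7, 4.7 and 4.7.5, and reconcile the 24-week serum in Section 4.7.1 with Section 4.9.3 and Appendix B for donors.

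The cost is redrafting and agreement on margins, for example by the regeneration workgroup. The analysis change needs no new data. The downside is that a tight margin, or much missing month-3 data, may leave the result inconclusive; that should then be reported as such.

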## 4.8. Secondary Aim 4: To evaluate differences in the immune response to LDLT vs. DDLT grafts.

1566

Living donor liver transplantation presents a unique immunological setting that is determined by three major variables that are different from the DDLT setting, with the potential to impact on short and long-term graft and patient survival, as well as recurrent disease:

- Regeneration may be associated with different pattern of lymphocyte trafficking in and out of the graft resulting in a differential repopulation of the liver with donor cells, and unknown effects on the extent of peripheral chimerism.
- Transplantation of a lobe from a living donor is done under conditions allowing extremely short cold ischemic time (60 vs. 500 minutes), a variable that may affect the severity of the inflammatory and immune response.
  - 3. We assume that 40% of LDLT are done between genetically related individuals, resulting in a potentially more favorable HLA matching.
- 1578 1579

1577

1580 Preliminary data demonstrate a potentially different alloimmune and antigen-specific 1581 immune response in recipients undergoing LDLT. Previous single center studies have suggested a reduced rate of rejection after adult-to-adult LDLT. Interestingly, there is a 1582 trend toward more rapid recurrence of hepatitis C infection, a phenomenon that may be 1583 1584 related to liver regeneration and/or inhibition of immune related anti-HCV response. The 1585 prospective cohort study will be designed to address whether LDLT affects mechanistic 1586 issues of liver transplantation immunobiology. The clinical findings will be correlated 1587 with specific laboratory assays, and will be compared with a control group undergoing 1588 DDLT transplantation. These findings will determine the opportunities for appropriate 1589 clinical modifications in the immunosuppression protocol, aiming at better outcomes for 1590 graft rejection and reduced frequency of recurrent disease. The clinical data and the 1591 specimens that are collected will be used to further support hypothesis-driven 1592 investigations, aiming to determine patterns of immune response and the potential 1593 development of favorable induction of tolerance, and those that are aiming to reduce the 1594 recurrence of the primary liver disease.

1595

To determine whether recipients of LDLT develop better immunological acceptance of the allograft when compared to recipients of DDLT allografts, the alloimmune response will be followed by a set of well-described clinical variables and pathology findings that are associated with acute and chronic rejection of the allograft:

1600 1601

1602 1603

1604

- 1. Time to rejection
  - 2. Frequency of rejection and recurrent rejection
  - 3. Severity of rejection as reported by liver biopsy
- 4. Frequency of steroid resistant rejection necessitating antibody therapy.
- 1605 5. The development of chronic rejection and graft loss.
- 1606 1607

#### 1608 **4.8.1. Study Methods**

1609 Common immunosuppression and rejection protocols:

1611 Guidelines:

- A common immunosuppression protocol will be used in order to allow an analysis of recipient outcomes as related to graft and patient survival, as well as recurrent disease.
- 16152. The proposed protocol is based on standard immunosuppression drugs that are currently being used in the liver transplant setting.
- 16173. Patient safety may require further adjustment for the proposed1618immunosuppression protocol.
- 1619

1610

- 1620 The standard immunosuppression protocol for the A2ALL study is shown in Table 1.
- 1621 The protocol includes adjustment for patients suffering from HCV infection.
- 16221623 The standard treatment for steroid-sensitive and steroid-resistant rejection is shown in
- 1624 Table 2. The protocol includes adjustment for patients suffering from HCV infection.
- 1625

1626 Adjustment in the calcineurin inhibitors (CNI) for patients who are suffering from renal 1627 insufficiency are presented in Table 3.

- 1628
- 1629
- 1630
- 1631 Table 1

Table 1.				
	Non	-HCV		HCV
	Tacrolimus	Prednisone	Tacrolimus	Prednisone (mg/d)
	(ng/ml)?	(mg/d)?	(ng/ml)	
OR		500		500
1 week	10	20	10	20
1 month	10	15	10	10
2 months	10	5	10	5
3 months	10	5	10	D/C
6 months	8	D/C for all patient except:	8	
		PSC,		
		Autoimmune,		
		PBC who are to		
		continue on 5		
		mg for the first		
		year, and 2.5		
		mg for the		
		second year.		
1 year	5-7		5-7	

Comments	The Prednisone	The Prednisone is
	is tapered in the	tapered in the first
	first week (see	week (see below) to
	below) to 20	20 mg/day.
	mg/day.	Reduction in
	Reduction in	prednisone is by 2.5
	Prednisone is	mg every one to two
	by 5 mg every	weeks.
	month.	

1632

- 1633 Tacrolimus will be started within the first 12 hours after surgery with the aim to achieve
- 1634 levels within the first 3 days.
- 16351636 Severe recurrence of hepatitis C may necessitate more rapid withdrawal of Prednisone
- 1637 and/or lowering tacrolimus levels to below the recommended above.

1638 1639

Table 2: Rejection Protocol

	Dradnisana
	Prednisone
Prednisone	In hospital: 1000-1500 mg total over a maximum of 3
For biopsy	days
proven	Outpatient taper:
rejection	200mg
	160mg
	120mg
	80mg
	40mg
	20mg
	Maintenance:
	follow the protocol as proposed in table 1 for HCV+
	and non-HCV patients.
Steroid-	Thymoglobulin: 1.5mg/kg daily for 5-7 days
resistant	
rejection	Thymoglobulin should be adjusted as per Center
-	protocol for reduced platelet and/or WBC counts.
(patient	
should have	
biopsy	
proven	
persistent	
rejection)	

1640 1641

1642

Table 3: Adjustment of immunosuppression in the presence of renal insufficiency

1. Creatinine levels between 2-3 will be managed by reduction of tacrolimus levels to the range of 5-7, and MMF at 1gr BID.

2. Creatinine >3 will be managed by calcineurin-free interval for 3 days with MMF 1.5gr

BID. After that time, tacrolimus level will be adjusted to achieve a level of 5-7, and MMF will be reduced to 1 gr BID.

3. Tacrolimus levels will be ajusted to those recommended in Table 1 once kidney function improves

1643

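### In Table 1 the non-HCV prednisone doses at 1, 2 and 3 months cannot be reached by the monthly taper stated in the same table

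*Protocol*

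**What the plan says.** Protocol section 4.8.1 gives one standard schedule and the reason for it: "A common immunosuppression protocol will be used in order to allow an analysis" of recipient outcomes. Table 1 splits the schedule by HCV status only; LDLT and DDLT recipients share it. After the time label, each row gives tacrolimus and prednisone for non-HCV recipients, then the same pair for HCV recipients:

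- "1 week 10 20 10 20"
- "1 month 10 15 10 10"
- "2 months 10 5 10 5"
- "3 months 10 5 10 D/C"

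At 6 months the non-HCV prednisone entry is "D/C for all patient except" three diagnosis groups (PSC, autoimmune, PBC), who stay on 5 mg through the first year and 2.5 mg through the second.

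The comments row adds a taper rule per column. Both columns come down to 20 mg/day in the first week. After that, the non-HCV dose falls by 5 mg each month. For HCV recipients the reduction in "prednisone is by 2.5" "mg every one to two" weeks.

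Table 2 sends patients treated for rejection back to Table 1 for their maintenance dose.

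**The concern.** The non-HCV column gives a dose at each time point and a rule for moving between time points, and the two disagree. A center that follows the rows and a center that follows the comment give different doses at 2 months, and possibly between 3 and 6 months. Because Table 2 refers back to Table 1, the same ambiguity reaches patients who have just been treated for rejection.

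Two things are at stake. One is clinical: an operative dosing instruction cannot be carried out as written. The other is analytic: Secondary Aim 4 compares LDLT with DDLT on time to rejection and on rejection in the first year (4.8.4 and 4.8.5), and 2 months lies inside that window. A schedule introduced to hold immunosuppression alike across nine centers leaves them to choose between two steroid doses.

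**Working it through.** **Inputs** (Table 1, 4.8.1, prednisone in mg/day)

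| Time | Non-HCV | HCV |
|---|---|---|
| 1 week | 20 | 20 |
| 1 month | 15 | 10 |
| 2 months | 5 | 5 |
| 3 months | 5 | stopped |
| 6 months | stopped, with exceptions | – |

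Rules: non-HCV, 5 mg per month; HCV, 2.5 mg every one to two weeks.

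**Non-HCV, nominal steps.** From 15 mg at 1 month the rule gives 15 − 5 = 10 at 2 months, 10 − 5 = 5 at 3 months and 5 − 5 = 0 at about 4 months. The rows fall by 15 − 5 = 10 mg between months 1 and 2, then by 5 − 5 = 0 mg between months 2 and 3. Starting instead from the listed 5 mg at 2 months, the rule gives 0 at 3 months against a listed 5.

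**Non-HCV, with loose timing.** Going from 20 to 5 mg takes (20 − 5)/5 = 3 cuts. The dose is 20 mg at 1 week, so the first cut falls on day 8 at the earliest. With cuts at least 28 days apart, the third falls no earlier than day 8 + 2 × 28 = 64. Two months is day 56, 60 or 61, depending on how a month is counted, so 5 mg at 2 months is out of reach. A grid of 3 month lengths × 4 spacings (28 to 31 days) × 24 first-cut days (8 to 31) = 288 schedules agrees: none gives 15 mg at 1 month and 5 mg at 2 months.

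**Non-HCV, after 3 months.** In the same grid, every schedule with 15 mg at 1 month is at 0 or 5 mg by 4 months and at 0 by 6 months. The table has no row between 3 and 6 months, and its 6-month entry presupposes patients still on treatment. This is a weaker tension, since the comment could be meant to apply only until 5 mg is reached, but the table does not say so.

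**HCV column.** From 20 mg to zero is 20/2.5 = 8 steps. Week 1 to month 3 is about 12 weeks, so 12/8 = 1.5 weeks per step, inside the stated range. Cuts on days 8, 15, 22 and 29 (weekly), then 43, 57, 71 and 85 (two-weekly), give:

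- day 7: 20
- day 30: 20 − 4 × 2.5 = 10
- day 60: 20 − 6 × 2.5 = 5
- day 90: 20 − 8 × 2.5 = 0

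Every entry is met. The 1-month value is tight: with a month of exactly 28 days only three cuts fit, giving 12.5 mg. Across the stated range the rule allows 10 to 17.5 mg at 1 month, 0 to 12.5 at 2 months and 0 to 7.5 at 3 months.

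**Recipients covered.** Sections 4.5.4 and 4.8.4 plan 360 LDLT + 355 DDLT = 715, and 4.5.4 assumes 30% with HCV. Non-HCV: 0.70 × 715 ≈ 500.

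**Power.** For 43% versus 56% with 360 and 355 recipients (4.8.4), the pooled proportion is 0.4945, the null standard error 0.0374 and the alternative standard error 0.0371. Then (0.13 − 1.96 × 0.0374)/0.0371 ≈ 1.53, a power of 0.937 against the stated 93%. The figure reproduces, and nothing in it depends on Table 1.

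**The case against.** The strongest reply is that this is one cell. The values 20, 15 and 5 at week 1, month 1 and month 3 all agree with 5 mg per month; only the 2-month entry departs, by 5 mg/day for about a month. The text was read from a PDF and the table's headings carry stray characters, so the cell may be misread. This stands in part. The size is modest and the page must be checked, but the four rows came through with every value in place.

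A second reply is that strict uniformity was never promised: 4.8.1 allows adjustment for safety, and section 4 calls the study primarily observational. That is true, but a permitted departure does not settle what the default dose is. The Manual of Operations (6.2) may already hold a clarification; it is not available here.

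The third reply concerns consequences and largely stands. A reader might infer that the common schedule is no longer common and that the LDLT versus DDLT comparison is biased. The documents do not support that. One table governs both groups, and 4.2.2 requires comparable numbers of LDLT and DDLT in each center, reviewed every 6 months with a procedure to correct shortfalls. Bias would need centers to resolve the conflict differently and also to differ in their enrolled LDLT:DDLT mix.

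**Conclusion.** The contradiction is real and confined to the non-HCV column: the entries at 1, 2 and 3 months and the monthly rule cannot both be followed, and they differ by 5 mg/day (5 against 10) at 2 months. There is a lesser mismatch between a taper that ends at about 4 months and a stop listed at 6. Up to about 500 of 715 planned recipients fall under the column. That is an upper bound: it rests on the protocol's 30% HCV assumption and counts every non-HCV recipient as affected.

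The consequence is ambiguous care and some added variability in the Secondary Aim 4 rejection comparison. No effect on rejection can be quantified from the documents, and no stated power changes.

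A reader might also infer that the HCV column contradicts its own rule and that Secondary Aim 1 suffers. It does not. That inference comes from testing only a fixed weekly or a fixed two-weekly pace, or from counting a month as exactly 28 days. The rule is a range, a schedule inside it meets every entry, and HCV recipients do not use the non-HCV column.

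The conclusion assumes that the 2-month row was read correctly from the page. It says nothing about which figure is right.

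**What to change.** 1. Check the non-HCV 2-month entry against the original page of Table 1.
2. If it stands, the Clinical Immunology Workgroup should reconcile the non-HCV entries with the taper comment, cover the interval from 3 to 6 months, and issue one consistent table. Because Table 2 refers back to Table 1, it then follows the same reading. The choice of dose is the workgroup's.
3. Record the prednisone dose actually given around months 1, 2 and 3 on the immunosuppression form already listed in 4.8.3, including for recipients already transplanted where the records allow, so that any difference between centers can be described.

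The cost is a protocol clarification, a matching entry in the Manual of Operations and a few dose fields on an existing form. Sample size, visits and planned analyses do not change.
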